6.2 Enrolment in the Trial

All patients with suspected CRVO attending one of the participating trial sites will be screened for eligibility. If a patient fails screening, i.e., does not meet all inclusion criteria or meets one or more of the exclusion criteria, the patient can be re-screened within 30 days once, if the reason(s) for the screening failure is (are) resolved.

If all inclusion criteria and no exclusion criteria apply and the patient provides written informed consent, a web-based randomisation (Day -14 to 0) will be performed and the patient will be assigned to a treatment arm. The patient ID has to be entered in the patient identification list (PIL) in the investigator site file together with the patient's name and date of birth. The randomisation result will be shown online by the randomisation tool and an automatic e-mail will be sent to the trial site for filing in the investigator site file (ISF). If a trial site prefers an automatic fax, this could also be implemented.

In cases, when the randomisation cannot be performed using the internet-based tool (server shut down, internet connection blocked ...), the randomisation page of the eCRF can be filled in by hand and sent to the ZKS Leipzig by e-mail (scan) or fax. There will be a randomisation list at the ZKS Leipzig allowing database independent randomisation during regular office hours (Monday – Friday, between 8:00 am and 5:00 pm). After such a randomisation, the patient will be entered to the database by the ZKS Leipzig as soon as the database is functional again.

Randomisation results and allocated treatment has to be documented in the patient's medical record.

The assessments and procedures essential for trial inclusion are described below.

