- **The best-corrected visual acuity (BCVA)** will be assessed in ETDRS letters. After “success” is reached (treatments free interval \geq 6 months) all patients will be seen at “mandatory visits” only. These visits are planned at: months 1 to 12, 16, 20, 24, and 29.
- **Visual field** measures are performed at month 4 and month 24 (at both visits in both eyes).

Objective assessment BCVA investigation will be performed by blinded BCVA assessors, who are independent of decisions regarding further re-treatment or other study procedures.

- **Neovascularisations** will be identified by gonioscopy, slit lamp bio-microscopy, ophthalmoscopy and/or FAG. A single occurrence during the entire duration of observation per patient will already contribute to the rate per arm, which will be compared between groups.
- **OCT-angiography** parameters as perfusion density and size of central avascular zone measurements will be at the baseline at month 4, 12, 24 and at month 29
- Patients will complete the **QoL questionnaire** before the ophthalmologic investigation will be performed at the baseline at month 12 and at month 24. Because QoL is a complementary aspect of the trial intervention only.

It is recommended to perform the ocular assessments in the order they are listed in each visit description.

Ocular assessments at the screening visit will be performed in both the study eye and the fellow eye (exception: gonioscopy).

All other ocular assessments at all other visits will only be performed in the study eye with exception of visual field (V4 and V24) and ophthalmoscopy at V24.

⇒ **For blood pressure, OCT, OCT-A, visual field and intraocular pressure (IOP) measurements, the same method must be used for all measurements throughout the study.**

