6.3.1 Screening visit (Day -14 to Day 0)

- Signed informed consent
- Medical history and ophthalmic history
- Assessment for women of childbearing potential: urine pregnancy test
- Blood pressure and pulse
- Ocular assessments (study eye and fellow eye):
 - Investigation of BCVA using ETDRS chart **performed by a blinded assessor**
 - IOP
 - Gonioscopy (exception: study eye only!)
 - Slit lamp biomicroscopy
 - OCT (in addition OCT will be evaluated by the CoRaLa II Central Reading Center)

- OCT-Angiography (in addition OCT-Angiography will be evaluated by the CoRaLa II Central Reading Center)
- Ophthalmoscopy
- Fundus photography and Fluorescein angiography (FAG) performed according to the imaging protocol and evaluated by the CoRaLa II Central Reading Center.

⇒ If all inclusion criteria and no exclusion criteria apply randomisation is performed.
 ⇒ **The screening visit may be performed together with Baseline Visit on the same day.**

6.3.2 Day 1 – Visit 1 (Baseline), Visit 2 (month 2 +/- 7 days) and Visit 3 (month 3 +/- 7 days)

- Blood pressure and pulse
- QoL (Visual Function Questionnaire) only at Baseline
- Documentation of Adverse events, critical ocular events and Concomitant medication
- Ocular assessment (assess prior to injection, assess in the study eye only):
 - Investigation of BCVA using ETDRS chart **performed by a blinded assessor**
 - IOP
 - Slit lamp biomicroscopy
 - OCT (in addition OCT will be evaluated by the CoRaLa II Central Reading Center)
 - Ophthalmoscopy
 - Fundus photography and Fluorescein angiography (FAG) performed according to the imaging protocol and evaluated by the CoRaLa II Central Reading Center, **only at Visit 3.**

➤ Control group:
 Ranibizumab injection at Baseline, Visit 2 and Visit 3.

➤ Experimental group:
 Ranibizumab injection at Baseline, Visit 2 and Visit 3.
ONLY at Visit 2 (Month 2) laser photocoagulation will be performed in the experimental arm before injection of Ranibizumab.

6.3.3 Visit 4 (month 4 +/- 7 days) Start of Maintenance dosing phase monthly Visits up to Visit 12 (month 12 +/- 7 days)

- Blood pressure and pulse

- QoL (Visual Function Questionnaire) only at Visit 12 before the ophthalmologic investigation will be performed
- Documentation of Adverse events, critical ocular events and Concomitant medication
- Ocular assessment (assess prior to injection, assess in the study eye only, see exceptions in text below):

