7 METHODS OF DIAGNOSTICS AND DATA SAMPLING

⇒ Best Corrected Visual Acuity (BCVA)

BCVA of the study eye (at screening performed in both eyes) will be assessed using the ETDRS chart (The Early Treatment Diabetic Retinopathy Study Group, 1985). The BCVA examiner will remain blinded to treatment allocation of a patient. A detailed protocol for conducting BCVA testing and refraction will be filed in the investigator site file. BCVA will be performed at all study visits.

⇒ Central subfield thickness (CST) measured by Optical Coherence Tomography (OCT)

Macular edema characteristics will be evaluated using OCT. All OCT images will be captured using the spectral domain (SD) OCT device and will be electronically archived. To ensure consistency and quality in image acquisition only experienced technicians will perform the OCT investigation using dense volume scans. OCT will be done at every study visit. A detailed protocol for OCT capturing and data transfer will be filed in the investigator site file. The measurement of the central subfield thickness (CST) and the total macular volume will be done by the CoRaLa II Central Reading Center.

⇒ Vessel Density (VD) and area of foveal avascular zone (FAZ) measured by Optical Coherence Tomography Angiography (OCT-A) – complementary outcomes

OCT-A imaging was performed after pupil dilatation. The same OCT-A device will be used for all single patients over all study visits. The macula will be imaged using 6x6 mm² scans. Additionally, peripheral OCT-A scans will be captured, too. A detailed protocol for OCT-A imaging will be filed in the investigator site file. The captured scans will be transferred to the CoRaLa II Central Reading Center, which will analyse the segmentation quality and measure the VD and the area of the foveal avascular zone (FAZ) in the superficial and deep vascular plexus.

⇒ **Peripheral Areas of non-perfusion (pANP – complementary outcome)**

Peripheral areas of non-perfusion will be measured by CoRaLa II Central Reading Center using the early stages of the FA images (arterial phase) captured by Clarus 700 device. The entire area will be measured in mm² using the device internal software based on the ratio of the peripheral non-perfusion to the area of the optic disc. Further, Greatest line dimension (GLD) of horizontal and vertical reference area (optic disc) will be calculated to ensure a valid assessment of area measurements over all measures performed in the course.

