9.2.3 Further complementary outcomes including quality of life

- proportion of subjects developing neovascularization(s) of retina, optic disc, and/or in anterior segment over the total period of observation.
- patient-reported health-related quality of life (QoL) will be investigated at BL and at the end of study. It is measured by the Visual Function Questionnaire VFQ25 [28], which focuses on functional aspects in case of impaired visual acuity. It has been proven to have satisfying properties regarding validity, reliability and sensitivity to change in English and German. Patients will complete the questionnaire before the ophthalmologic investigation will be performed at the baseline and at month 12 and 24. We expect most patients to understand the questions in the questionnaire.

Because QoL is a complementary endpoint only we refrain from having an exclusion criterion on language. The pre-post change in the QoL will be analysed.

- vessel density (assessed by OCT-angiography, see also sec. 7) will be quantified by a metric measure with the range [0;1].
- area of the foveal avascular zone (FAZ, assessed by OCT-angiography, see also sec. 7, in [mm²])
- the area of non-perfusion (assessed by FA) will be quantified as sum of all areas identified (see also sec. 7);
- a potential visual field loss will be quantified as follows: for each patient the retinal sensitivities over all points tested will be summed-up and divided by the number of points investigated. The harmonized mean per group will be calculated per group and visit. The change between the two timepoints (Months 4 and 24) per arm will be used to characterize the both groups and be compared between treatment arms (see also sec. 7);
- the number of visits with applied laser treatment and the laser spots applied in the experimental group (RL-arm) will be counted for descriptive reasons and be compared between treatment arms.

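### The baseline VFQ-25 is scheduled after randomisation, with no patient masking described, so the reference value for the quality-of-life change can reflect knowledge of the arm

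*Protocol*

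**What the plan says.** Section 6.2 states that "a web-based randomisation (Day -14 to 0) will be performed and the patient will be assigned to a treatment arm". Section 6.3.1 makes this the closing step of the screening visit: "If all inclusion criteria and no exclusion criteria apply randomisation is performed". The procedures listed there contain no questionnaire. On disclosure, section 6.2 says: "The randomisation result will be shown online by the randomisation tool". The result is also e-mailed to the site and must be entered in the patient's medical record.

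The VFQ-25 first appears in section 6.3.2, at Day 1 / Visit 1: "QoL (Visual Function Questionnaire) only at Baseline". The schedule of assessments agrees: randomisation is marked under screening and the first questionnaire under V1.

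The protocol sets one ordering rule for the form. In section 6.3 it is to be completed "before the ophthalmologic investigation will be performed at the baseline at month 12 and at month 24", and section 9.2.3 repeats this. A combined visit is allowed: "The screening visit may be performed together with Baseline Visit on the same day".

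On masking, section 7 says: "The BCVA examiner will remain blinded to treatment allocation of a patient". Sections 3.2.1 and 6.3 likewise describe blinding for the acuity assessor only.

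Section 9.2.3 says that the pre-post change in quality of life will be analysed, and calls the outcome complementary.

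**The concern.** A baseline is useful as a reference because it is fixed before allocation, so that the arms can differ on it only by chance. A self-report collected after allocation, from patients who are not masked as far as the protocol describes, loses that guarantee. Disappointment at receiving injections alone, or optimism or worry about added laser, could move the answers before any treatment is given. The protocol itself expects laser to benefit quality of life (sections 1.1 and 1.2.1), and consent covers the trial's objectives and benefits (section 6.1), so expectation is a plausible route.

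A shifted baseline enters every change score, at month 12 and month 24 alike, because both use the same reference. A model adjusted for baseline reduces the effect but does not remove it. A value that was never collected before allocation cannot be recovered in the analysis.

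**Working it through.** No figure in the protocol depends on this point, so there is none to reproduce. The check is of the order of procedures, followed by an illustration of how a shift would pass into the result.

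**Order of procedures**

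- Separate visits: consent and screening eye examination, randomisation (day -14 to 0), allocation shown to the site, then Visit 1 with the VFQ-25, up to about two weeks later. The form is after randomisation by design.
- Combined visit: the form must precede the eye examination, and the screening eye examination must precede randomisation because eligibility depends on it. If the form precedes the screening examination, it is before allocation. But Visit 1 has its own ocular assessment, and the text does not say which examination the rule refers to when the visits are merged. Either order complies.
- Treatment before the form: none. The first injection is at Visit 1 and the first laser at month 2, so any shift acts through expectation alone.

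**How a shift enters the result**

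Let d0 be the between-arm shift at baseline caused by knowing the arm, d1 the corresponding shift at follow-up, and b the slope on baseline in an adjusted model.

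- Bias in the change-score contrast: d1 - d0.
- Bias in the baseline-adjusted contrast: d1 - b·d0.
- Bias in either contrast with a pre-randomisation baseline (d0 = 0): d1.

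If the whole effect persists (d1 = d0), it cancels in the change score. If half persists, half remains. If it has vanished by follow-up (d1 = 0), the change-score bias is -d0 in full.

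**Illustration, least favourable case d1 = 0**

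Inputs: 110 patients (section 3.3) allocated 1:1 (section 3.1), hence 55 per arm. Everything else is assumed, because the documents give no VFQ-25 standard deviation and no shift: SD of the change score 10 to 20 points, no true difference at follow-up, two-sided 5% test.

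SE = SD × √(2/55) = SD × 0.1907, so 1.91 points at SD 10 and 3.81 points at SD 20.

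False-positive rate = Φ(-1.96 + d0/SE) + Φ(-1.96 - d0/SE).

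| Assumed net shift (points) | Change-score bias | Error rate, SD 20 | Error rate, SD 10 |
|---|---|---|---|
| 1 | -1 | 6% | 8% |
| 2 | -2 | 8% | 18% |
| 3 | -3 | 12% | 35% |
| 5 | -5 | 26% | 75% |

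For example, 2 points at SD 10: 2/1.907 = 1.049, and Φ(-0.911) + Φ(-3.009) = 0.18. If half of a 2-point shift persists, the net shift is 1 point and the first row applies. Adjustment with an assumed b of 0.5 halves the bias when d1 = 0 (2 points become 1). The table shows sensitivity only; it does not estimate what will happen in this trial.

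**The case against.** The case against has force on several counts.

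- A reader might infer that all 110 patients have a post-allocation baseline. The documents do not support that. Combined visits are allowed, and the order rule can put the form before randomisation on such a visit. The split between combined and separate visits is not given.
- A reader might take it as stated that patients know their arm at Visit 1. The protocol says when the site learns it, not when the patient does. Both arms have the same injection at Visit 1 and laser starts at month 2. Disclosure by then is likely, since nothing withholds it, but it is an inference.
- A reader might credit the protocol with requiring the form before the eye examination in order to protect the answers, and then call it inconsistent. It gives no reason for the rule, so that contrast should not be drawn.
- A reader might attach a definite bias of a few points at months 12 and 24. No size or direction can be derived from the documents, and a persistent expectation effect would partly or wholly cancel in the change score. In that case moving the baseline leaves the follow-up shift fully exposed.
- The outcome is complementary. Time to treatment success, visual acuity, retinal thickness and injection counts are untouched.
- Recruitment began in August 2020 (section 3.4), so a change now gives a baseline of mixed timing.

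These points limit the reach and size of the problem. They do not remove it: with separate visits the form follows randomisation, and no rule protects it from knowledge of the arm. Cancellation cannot be relied on either, since it needs the same shift at Visit 1 and at follow-up one to two years later.

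**Conclusion.** The point holds in a limited form. The baseline VFQ-25 is taken after randomisation whenever screening and Visit 1 are on different days, and may be on combined visits, so the reference for the quality-of-life change can reflect knowledge of the allocated arm. This rests on two readings: that patients are not masked (only the acuity assessor is described as blinded, and no sham is described), and that they may learn their arm before completing the form.

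The size is unknown. Under the stated assumptions, a net shift of 1 to 3 points would raise a 5% error rate to between 6% and 35%; a net shift of zero would leave it at 5%. The consequence is confined to one complementary outcome. It is a modest flaw, worth correcting because the correction is cheap. It gives no reason to doubt the confirmatory analysis.

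**What to change.** Have the baseline VFQ-25 completed after consent and before both the ophthalmic examination and randomisation. On combined visits, require completion before the allocation is retrieved. Align the schedule of assessments and sections 6.3, 6.3.1, 6.3.2 and 9.2.3.

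For patients already enrolled, record whether the questionnaire preceded randomisation, asking the site where both fell on the same day, and report a sensitivity analysis of the quality-of-life change by that status.

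The cost is one existing form moved to an existing visit. About 20 screen failures (130 assessed less 110 allocated) would also complete it, and the timing of the baseline would differ between patients enrolled before and after the change. The change secures an untouched reference value only. It does not remove bias from unmasked reporting at months 12 and 24, and the report should say so when it presents this outcome.

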6.5 Premature Termination of the Therapy and Follow-up for Individual Patients

6.5.1 Premature Termination of the Therapy for Individual Patients

Each premature termination of the trial therapy has to be documented by the responsible investigator. If possible, date, circumstances of and reason for the termination should be documented in detail and communicated to the ZKS Leipzig Data Management. Premature termination should be avoided.

The premature termination of trial therapy for an individual patient may be considered for the following aspects:

- progress of neovascular complication (Increase of NVE's or NVD's, neovascular glaucoma) (see rescue treatment)
- persisting macular edema without response to Ranibizumab
- protocol violations if they indicate a significant risk to the patient's safety
- non-compliance
- pregnancy

- at the discretion of the investigator
- for reasons of medical prudence based on DSMB recommendations or
- withdrawal of consent

All patients with premature therapy termination (except in case of consent withdrawal) will, however, be instructed to return for a safety follow-up visit 4 weeks after last study treatment. Further, all patients (except in case of consent withdrawal) will be offered the visit in Month 29, because at this visit the primary endpoint is documented as well as the major secondary endpoints.

6.5.2 Rescue Treatment

Patients with progress of neovascular complication (Increase of NVE's or NVD's, neovascular glaucoma) will receive rescue treatment with pan-retinal photocoagulation (PRP) outside the study intervention.

Patients with persisting macular edema without response to Ranibizumab will be treated with intravitreal Aflibercept (Eylea) or dexamethasone implant (Ozurdex) out of the study.

6.6 Plan for Further Treatment

In case the patients will suffer from a recurrence of macular edema with impaired BCVA after month 23 (End of treatment visit) of the study, further treatment with anti-VEGF drugs (Ranibizumab or Aflibercept) or other treatment methods (e.g. application of Dexamethasone implant = Ozurdex) will be offered depending on investigators decision.

7 METHODS OF DIAGNOSTICS AND DATA SAMPLING

⇒ Best Corrected Visual Acuity (BCVA)

BCVA of the study eye (at screening performed in both eyes) will be assessed using the ETDRS chart (The Early Treatment Diabetic Retinopathy Study Group, 1985). The BCVA examiner will remain blinded to treatment allocation of a patient. A detailed protocol for conducting BCVA testing and refraction will be filed in the investigator site file. BCVA will be performed at all study visits.

⇒ Central subfield thickness (CST) measured by Optical Coherence Tomography (OCT)

Macular edema characteristics will be evaluated using OCT. All OCT images will be captured using the spectral domain (SD) OCT device and will be electronically archived. To ensure consistency and quality in image acquisition only experienced technicians will perform the OCT investigation using dense volume scans. OCT will be done at every study visit. A detailed protocol for OCT capturing and data transfer will be filed in the investigator site file. The measurement of the central subfield thickness (CST) and the total macular volume will be done by the CoRaLa II Central Reading Center.

⇒ Vessel Density (VD) and area of foveal avascular zone (FAZ) measured by Optical Coherence Tomography Angiography (OCT-A) – complementary outcomes

OCT-A imaging was performed after pupil dilatation. The same OCT-A device will be used for all single patients over all study visits. The macula will be imaged using 6x6 mm² scans. Additionally, peripheral OCT-A scans will be captured, too. A detailed protocol for OCT-A imaging will be filed in the investigator site file. The captured scans will be transferred to the CoRaLa II Central Reading Center, which will analyse the segmentation quality and measure the VD and the area of the foveal avascular zone (FAZ) in the superficial and deep vascular plexus.

⇒ **Peripheral Areas of non-perfusion (pANP – complementary outcome)**

Peripheral areas of non-perfusion will be measured by CoRaLa II Central Reading Center using the early stages of the FA images (arterial phase) captured by Clarus 700 device. The entire area will be measured in mm² using the device internal software based on the ratio of the peripheral non-perfusion to the area of the optic disc. Further, Greatest line dimension (GLD) of horizontal and vertical reference area (optic disc) will be calculated to ensure a valid assessment of area measurements over all measures performed in the course.

⇒ **Defects of peripheral Visual fields (VF – complementary outcome)**

The visual field defects will be captured by assessing the retinal sensitivities of various points in the mid-peripheral and peripheral visual fields at month 4 and 24 in both eyes. Eyes with excessive false positive response or excessive fixation loss will be excluded from analysis.

A false positive response is defined as a response to a false positive test, i.e. a projector movement (or other external stimulus) when no stimulus is presented. Excessive false positive response is defined as [(# false positive responses) ÷ (# false positive tests)] *100 >33%.

A fixation loss is defined as a response to a fixation loss test, i.e. a stimulus presented to the blind spot. Excessive fixation loss was defined as [(# fixation losses) ÷ (# fixation loss tests)]*100 > 33%. Outlying values will be truncated at ±3 standard deviation from the mean to minimize the effect of potential outliers.

⇒ **Number of Ranibizumab injections**

All patients will receive 3 intraocular injections. The application of further injections is guided by standardized retreatment criteria. The number of injections required will be recorded for every patient.

⇒ **The progression to neovascularization of the retina or anterior segment**

Patients will be evaluated for the development of neovascularization of the iridocorneal angle by gonioscopy in conjunction with slit lamp biomicroscopy at screening visit and further at month 12 and 24. The examination should be performed after OCT and before funduscopy, fundus photography, and fluorescein angiography.

All patients will be investigated for the development of neovascularization of the optic disc or of the retina elsewhere by ophthalmoscopy in mydriasis at every visit. The presence of neovascularization will be documented by fundus photography. If suspected lesion could not be surely distinguished between neovascularization or shunt vessels by ophthalmoscopy, a fluorescein angiography will be performed.

Patients in whom a neovascularization will be found will undergo panretinal scatter laser photocoagulation as a rescue treatment according the recommendations of CRVO study group [24].

